#### 9.2.2 Clinical Global Impression Scale - Domain Improvement Scores

CGI-I assessments are completed at Visit 9 (Week 6), End of Treatment (Week 13, Visit 16), and Follow-up (Visit 17). The clinician rates how much the subject's illness has improved or worsened relative to Visit 3 (Week 0). The seven domain improvement scores are: Language/Communication, Social Interaction, Ambulation/Gross Motor, Fine Motor Functioning/Self-Help, Gastrointestinal, Autonomic/Breathing Abnormalities, and Challenging Behaviors: Repetitive Behavior/Self-Injury/Aggression. The individual domain CGI-I scores are rated on a 7-point scale, where 1='very much improved';

2='much improved'; 3='minimally improved'; 4='no change'; 5='minimally worse'; 6='much worse'; 7='very much worse'. Scores of 1, 2, and 3 indicate improvement. If a domain score is missing, that subject will be excluded from analysis for that domain.

Within subject change is indicated by the score at each relevant follow-up visit (Week 6, Visit 9 and Week 13, EOT, Visit 16). If a domain score is missing, that subject will be excluded from analysis for that domain at the relevant visit. The domain scores will be presented in figures as described in Section 9.2. Domain scores at EOT will be presented in a forest plot. Domain scores will be presented as line graphs at post-baseline visits.

Domain scores as reported on the CRF will be summarized at each post-baseline visit, in the same manner as the CGI-I Overall Score.

### 9.2.3 Caregiver Impression of Change Score

The Caregiver Impression of Change assessment will be completed at the end of treatment visit (Week 13, Visit 16).

The caregiver is asked to rate the change in his or her child's overall function and wellbeing since Visit 3 (Week 0), and the change in specific symptoms. This is rated on a 7point Likert scale: 1-Very much improved, 2-Much improved, 3-Improved, 4-Unchanged, 5-Worse, 6-Much worse, 7-Very much worse. Scores of 1, 2 or 3 indicate improvement in overall function and symptoms.

The assessment of change should be made relative to Visit 3 (Week 0). The caregiver should assess the subject's current state at the visit taking into consideration observations at the visit and symptoms within the last week.

For the rating of overall function, the caregiver also identifies the one symptom area or feature that has most influenced his or her rating of the child's overall function and provides a description of symptom changes and impact of the changes.

The symptom domains rated are: communication, social interaction, behavior, motor abilities, seizures, cognition and learning, self-care, gastrointestinal (GI) problems, and breathing problems. Within subject change is indicated by the score at EOT. If a score is missing for a domain, that subject will be excluded from the corresponding domain summaries.

Summary statistics on the Caregiver Impression of Change overall and domain scores will be displayed at End of Treatment. The overall score will be presented in waterfall plots, and histograms or bar charts (as appropriate), and the domain scores will be presented in a forest plot, as described in Section 9.2.

### 9.2.4 Clinical Global Impression Scale - Severity - Overall Severity Score

Clinical Global Impression of Severity assessments will be made at the Screening visit (Visit 1), Visit 3 (Week 0), Visit 9 (Week 6), End of Treatment (Week 13, Visit 16), and Follow-up (Week 15, Visit 17). The overall severity score is scored on a 7-point scale, where 1='typical for age, not at all impaired'; 2='borderline, slightly impaired'; 3='mildly impaired'; 4='moderately impaired'; 5='markedly impaired'; 6='severely impaired'; 7='among the most severely impaired'. Lower scores reflect less impairment. Within subject change is the difference between the score at each relevant follow-up visit and the score at baseline. If a score is missing, the subject will be excluded from the corresponding summaries.

The overall score and change from baseline at each post-baseline visit will be summarized using descriptive statistics. Within subject changes will be analyzed using a Wilcoxon signed rank test at Week 6 and EOT. Test-retest reliability will be assessed for all scores collected during the Screening period (Visits 1 and 3) using ICC. The change from baseline in the overall score at EOT will be presented in figures as described in Section 9.2. The overall score will also be presented as a line graph at post-baseline visits.

### 9.2.5 Clinical Global Impression Scale - Severity - Domain Severity Scores

The CGI-S assessments will be made at the Screening visit (Visit 1), Visit 3 (Week 0), Visit 9 (Week 6), End of Treatment (Week 13, Visit 16), and Follow-up (Week 15, Visit 17). The seven domain severity scores are: Language/Communication, Social Interaction, Ambulation/Gross Motor, Fine Motor/Self-Help, Gastrointestinal, Autonomic/Breathing Abnormalities, and Challenging Behaviors: Repetitive Behavior/Self-Injury/Aggression. Each domain score is scored on a 7-point scale, where 1='typical for age, not at all impaired'; 2='borderline, slightly impaired'; 3='mildly impaired'; 4='moderately impaired'; 5='markedly impaired'; 6='severely impaired'; 7='among the most severely impaired'. Lower scores reflect less impairment. Within subject change is the difference between the total score at each relevant follow-up visit and the score at baseline. If a score is missing, the subject will be excluded from the corresponding summaries.

The change from baseline in CGI-S domain scores will be analyzed in the same manner as the CGI-S overall score. The change from baseline in domain scores at EOT will be presented in forest plots as described in Section 9.2. Domain scores will be presented as line graphs at post-baseline visits.

#### 9.2.6 MacArthur-Bates Communicative Development Inventory Scores

The MB-CDI will be completed at Visit 3 (Week 0) and End of Treatment (Week 13, Visit 16). This caregiver-completed instrument assesses language development in vocabulary comprehension and production, gestures, and grammar. Designed to assess early language development in infants and toddlers, it can also be used with older, developmentally delayed children to assess developmental progress in language development. The MB-CDI includes three modules based on chronological or developmental age: Words and Gestures (8 to 18 months or developmental equivalent), Words and Sentences (16 to 30 months or developmental equivalent) and the CDI-III, an extension of the MB-CDI used with children 30 to 37 months (or developmental equivalent). Only the Words and Gestures module will be used for this study in line with the cognitive and language development of the patient population.

The number of "yes" answers in "First signs of understanding" and "sometimes" and "often" in "Starting to Talk" will be summarized. The number of phrases understood, the number of words understood, number of words produced, number of early gestures, number of later gestures, and number of gestures will be summarized. For these scores, scores calculated by the site rater and entered in the EDC will be used for the analysis. Scores may also be derived if the EDC score calculations were not completed. The calculations are as follows:

- Phrases understood: total count of phrases selected in "Phrases" section (total phrases 28)
- Words Understood: total count of words selected as either "understands" or "understands and says" in the "Vocabulary Checklist". If for any given word both "understands" and "understands and says" are selected, the word is counted only once. Blanks are not counted. Total words 396.
- Words Produced: total count of words selected as "understands and says". If for any given word both "understands" and "understands and says" are selected, the word is counted only once. Blanks are not counted. Total words 396.
- Early Gestures: total count of "sometimes" and "often" responses in "First Communicative Gestures" and "yes" answers in "Games and Routines". 18 maximum.
- Later Gestures: total count of "yes" answers in "Actions with Objects," "Pretending to be a Parent," and "Imitating Other Adult Actions". 45 maximum.
- Total Gestures: Total of Early Gestures and Later Gesture scores. 63 maximum.

Change from baseline for the scores will be analyzed using a Wilcoxon signed rank test. The change from baseline in the "words understood" score and the "words produced score" at EOT will be presented in plots as described in Section 9.2. Exemplars of new words may be listed for individual subjects who show increases in vocabulary from baseline based on an increase in number of words produced.

### 9.2.7 Observer-Reported Communication Ability Score

The ORCA measure will be completed at Visit 3 (Week 0) and End of Treatment (Week 13, Visit 16). This caregiver-reported measure was developed to assess communicative abilities in verbal and low-verbal/non-verbal populations. The caregiver evaluates the individual's observed communication ability over the past 30 days. The ORCA measure will be scored using the R program provided by the ORCA developers (Center for Health Measurement, Duke University). The macro will produce an ORCA t-score as long as at least one of the 20 concepts or items has a score. A concept score will be given only if all items within the concept are answered. Higher scores reflect greater communication ability. The ORCA t-score range is 25.8 to 83.8.

Alterative scoring algorithms are in the process of being developed by the ORCA developers based on feedback from users in the research community. These alternative algorithms would provide scoring alternatives to provide credit for emerging skills in addition to mastery of skills. These algorithms are in development and are not yet available from the ORCA developers. In line with these approaches, a modified t-score will also be calculated as an exploratory measure. The SAS macro used to calculate the total score will be edited to give credit for both "always" and "sometimes" responses (to assess emerging skills). This modification to the analysis of the items will be used to calculate the modified t-score.

The t-score and modified t-score will be summarized using descriptive statistics. Change from baseline will be analyzed using a Wilcoxon signed rank test. The change from baseline in the t-score and modified t-score at EOT will be presented in plots as described in Section 9.2.

### 9.2.8 Caregiver Top 3 Concerns Rating

The Caregiver Top 3 Concerns Rating assessment will be completed at all Screening/Baseline period visits (Visits 1, 2, 3), as well as Week 6 (Visit 9), End of Treatment (Week 13, Visit 16), and Follow-up (Visit 17). The three concerns identified at Screening/Baseline are carried forward and rated at the follow-up visits.

Caregivers are asked to identify 3 concerns from among 11 clinically important symptom domains: Language/Communication, Social interest/Avoidance, Repetitive Behaviors, Challenging Behaviors, Gross motor skills, Fine motor skills, Gastrointestinal problems, Breathing Disruptions, Sleep, Seizures, and Self-care skills. Each individual concern identified should be from a different symptom domain, but caregivers can select any domain and choose any symptom of concern within that domain.

The severity of each concern is scored using a 10-point Likert scale of severity. Average Top 3 concern severity is defined as the average of severity scores for the three concerns. Lower scores indicate lesser severity. The average score (i.e., average of the severity scores for the Top 3 concerns) will have a range of 0 to 10. Improvement in concern average severity is defined as a change from baseline score < 0.

If the caregiver does not list the same 3 concerns on the Top 3 Concerns Follow-Up CRF that were recorded on the Top 3 Concerns Screening CRF (completed at Visit 1), then their responses will be reviewed and may not be included in analysis. A review of all concerns will be done prior to database lock, and visits with incorrect concerns will be flagged as unusable for analysis.

The frequency of any symptom being chosen for all concerns combined will be summarized. Summary statistics for the change from baseline in the average severity and by symptom domain will be displayed at all post-baseline visits. Change from baseline will be analyzed using a Wilcoxon signed rank test at Week 6 and EOT. The frequency of subjects with improvement in the concern severity will be summarized by average concern and symptom domain. Test-retest reliability will be assessed for all scores collected during the Screening period (Visits 1, 2, and 3, pre-dosing) using ICC. The change from baseline in the average concern severity at EOT will be presented in plots, as described in Section 9.2. The change from baseline in domain severity scores at EOT will be presented in a forest plot. The domain and average concern severity will be presented in line graphs at each visit.

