9.5.9.6 Caregiver Top 3 Concerns Rating

The Caregiver Top 3 Concerns Rating assessment is a syndrome-specific measure of 3 signs or symptoms of PTHS identified by caregivers at Screening/Baseline as being priority concerns in which they would like to see improvement as a result of treatment. The assessment will be completed at all Screening and Baseline visits (Visits 1, 2, 3), as well as Week 6 (Visit 9), EOT (Visit 16), and Follow-up (Visit 17).

In this assessment, concerns are identified on an individual, per-participant basis. The clinician should review the assessment with the caregiver at the Screening visit, ideally as part of the overall medical and clinical history. Caregivers should be encouraged, in selecting the concerns, to identify distinct, observable symptoms rather than broad ones. And caregivers should be advised to consider symptoms that they feel are important and have an impact on their child's daily functioning and well-being.

Caregivers are asked to identify 3 concerns from among 11 clinically important symptom domains: Language/Communication, Social interest/avoidance, Repetitive Behaviors, Challenging Behaviors, Gross motor skills, Fine motor skills, Gastrointestinal problems, Breathing Disruptions, Sleep, Seizures, and Self-care skills. Each individual concern identified should be from a different symptom domain, but caregivers can select any domain and choose any symptom of concern within that domain. The same three concerns identified at screening/baseline are carried forward and rated at the follow-up visits. The severity of each concern is scored by caregivers using a 10-point Likert scale or severity. The caregiver should give consideration to symptoms within the last two weeks.

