#### 2.2 Study Design

This is a Phase 2, open-label study of the safety and tolerability of NNZ-2591 Oral Solution, 50mg/mL IMP in male and female children and adolescents with Pitt-Hopkins syndrome. Approximately 10-20 male and female subjects between the ages of 3 and 17 years were planned to be enrolled and receive treatment of NNZ-2591 Oral Solution, 50mg/mL IMP for a total of 13 weeks.

There will be a total of 17 study visits, comprising 5 in-clinic visits and 12 remote telemedicine/in-home nurse visits. The study will commence with an approximately 4-6 week Screening and Baseline period. During this Screening/Baseline period, subjects are assessed for study eligibility and data is collected to establish the subject's baseline characteristics and symptom severity using a variety of assessments. Two in-clinic visits and one remote/in-home visit (Visits 1, 2, 3) comprise Screening and Baseline.

Once eligibility is confirmed, subjects are dosed with the starting dose of 4 mg/kg and then be up-titrated to the target dose. Subjects receive IMP for a total of 13 weeks. During the treatment period, there are three in-clinic visits: Week 2 (Visit 5), Week 6 (Visit 9) and Week 13 (Visit 16). There is a combined telemedicine/in-home visit by the site Investigator and an in-home visit by a visiting nurse for safety at Week 1 (Visit 4), Week 4 (Visit 7), Week 8 (Visit 11) and Week 10 (Visit 13). Ideally, these combination telemedicine/in-home visits will be conducted simultaneously whenever possible, or they will be conducted on the same day with the telemedicine visit occurring first. If this is not feasible the in-home and telemedicine components can be conducted over two consecutive days. In-home visits with a visiting nurse will be done at Weeks 3 (Visit 6), 5 (Visit 8), 7 (Visit 10), 9 (Visit 12), 11 (Visit 14), and 12 (Visit 15).

All subjects will also have a combined telemedicine/in-home follow-up visit with the Investigator via telemedicine and an in-person home visit by a visiting nurse approximately 2 weeks after the end of treatment (Week 15, Visit 17).

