### 5.2.5 Post-Baseline Values

For subjects who discontinue the study, data will be analyzed up to the last observation for safety and efficacy measures. Missing data for safety assessments will not be imputed. For efficacy rating scale measures other than the exceptions listed below, if an assessment has been completed but has missing items, missing values shall be imputed as follows:

- If 3 or fewer items are missing, the last observation for that particular data element (e.g., item response) will be carried forward.
- The scoring algorithms will be applied including the observed values and last observation carried forward (LOCF) for the missing items

These rules will only apply to individual items. Total scores, subdomain and subscale scores will not be carried forward. If the assessment is completely missing, items will not be imputed.

These imputation rules do not apply to the CGI-I, Clinical Global Impression Scale – Severity (CGI-S) or Caregiver Impression of Change assessments. If a particular domain is missing for these assessments, the participant will be excluded from the corresponding analysis. These imputation rules also do not apply to the Caregiver Top 3 Concerns assessment. If a concern is missing for this assessment, the average severity will still be calculated from all non-missing concern severity scores.

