A correlation analysis of the efficacy measures will be done using Pearson correlation coefficients at Baseline and EOT. The correlation of each total score will be measured against the others and presented in a table and a heat map/matrix. CGI-I and CGI-S domain scores will also be included in the correlation analysis. Test-retest reliability will be assessed for continuous efficacy assessments collected more than once during the Screening period (Visits 1, 2, and 3, pre-dosing) using Intraclass Correlation Coefficients

Statistical Analysis Plan 30APR2024

(ICC). The ICC will be based on covariance parameter estimates from a Restricted Maximum Likelihood Mixed Model including results from assessments conducted during the Screening/Baseline period with a random effect for subject. The ICC will be derived as: ICC = Within-subject covariance/Total covariance. ICC values range from 0 to 1, with values closer to 1 indicating greater test-retest reliability.

A treatment policy estimand will be used for all endpoints. The variables of interest are numeric scores associated with subject responses. Summaries will be performed on the observed data. There will be no imputations for completely missing scores or intercurrent events. Handling of missing responses items that contribute to total and subscale scores are defined in Section 5.2.5.

Results for each efficacy variable will also be listed by subject.

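### SAP 9.2.8 can discard a whole Top 3 Concerns visit over one non-matching concern, under an undefined rule that is stricter than the SAP's own rule for a blank concern

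*SAP*

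**What the plan says.** Protocol 9.5.9.6 sets the design: "The same three concerns identified at screening/baseline are carried forward and rated at the follow-up visits". SAP 9.2.8 repeats it, then provides for departures. If the concerns on the Follow-Up form are not the same three as on the Screening form completed at Visit 1, "then their responses will be reviewed and may not be included in analysis". The next sentence reads: "A review of all concerns will be done prior to database lock", and "visits with incorrect concerns will be flagged as unusable for analysis".

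SAP 5.2.5 covers a blank concern: "If a concern is missing for this assessment, the average severity will still be calculated from all non-missing concern severity scores".

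SAP 9.2.8 analyses the average severity and also each symptom domain: change from baseline, frequency of improvement, and a forest plot by domain. On testing it says: "Change from baseline will be analyzed using a Wilcoxon signed rank test at Week 6 and EOT". SAP 5.3 counts any change below 0 as improvement. The published SAP addendum does not revise 9.2.8 or 5.2.5.

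**The concern.** Four features of the rule are unsatisfactory.

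- **Two verbs.** Differing responses *may* be left out; visits with incorrect concerns *will* be flagged. The text does not say how a differing concern becomes an incorrect one. Rewording, a different symptom in the same domain and a different domain could each be treated either way.
- **Wrong unit.** One non-matching concern puts the visit at risk, including ratings of concerns that match Visit 1.
- **Open discretion.** No reviewer or criteria are named, and nothing says whether severity scores are hidden. The decision comes after the outcomes are recorded, on a caregiver rating in an open-label single-arm study.
- **Inconsistency.** A child with two matching ratings and an empty third line stays in. A child with the same two ratings and a different third concern can go out. No reason is given.

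At stake are valid ratings in a trial of about 10 to 20 children, and confidence that inclusion did not depend on the scores.

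**Working it through.** **The plan's own figures.** The SAP gives no standard deviation, effect or mismatch rate for Top 3 Concerns. Its only power figures (SAP 5.1) are for the CGI-I: SD 0.7, two-sided 0.05, Wilcoxon signed rank. They reproduce with power = 1 - F(t(0.975, n-1)), where F is the noncentral t distribution with n-1 degrees of freedom and noncentrality d√n, and n is the sample size times 3/π, rounded down.

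- 10 × 3/π = 9.55, so n = 9: detectable differences 0.747, 0.800, 0.866 (stated 0.75, 0.80, 0.87).
- 20 × 3/π = 19.1, so n = 19: 0.476, 0.509, 0.551 (stated 0.48, 0.51, 0.55).

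They say nothing directly about this measure.

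**The two rules side by side**, for a visit with two concerns validly rated and matching Visit 1:

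| Third line | Rule | Ratings kept |
|---|---|---|
| Blank | SAP 5.2.5 | 2 |
| Different concern, visit flagged | SAP 9.2.8 | 0 |
| Different concern, concern-level matching | proposed | 2 |

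**Ratings lost.** Assume one wrong concern per affected visit. For k visits, the visit-level flag discards 3k ratings and concern-level matching discards k. For k = 2 that is 6 against 2: of 30 ratings with 10 children (20% against 6.7%), or of 60 with 20 children (10% against 3.3%). Each flagged visit also removes one pair from the test, which is 10% or 5% of the pairs.

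**What losing pairs costs.** Borrow the CGI-I standardised effects (0.87/0.7 = 1.24 and 0.55/0.7 = 0.79) purely for scale, and assume loss at random. A simulation of the exact Wilcoxon test (40,000 runs, normal data) gives power 0.92, 0.86 and 0.80 with 0, 1 and 2 of 10 pairs lost, and 0.90, 0.89 and 0.86 with 0, 1 and 2 of 20 lost.

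**The blank-concern average.** Take assumed baseline scores of 9, 6, 6, mean 7. Nothing changes, but the concern scored 9 is blank at follow-up. The follow-up mean is (6 + 6)/2 = 6, so the recorded change is 6 - 7 = -1.0, which counts as improvement. In general the false change is (B - x)/2, where B is the baseline mean of all three and x is the baseline score of the missing concern. If one of the 6s is blank instead, it is (7 - 6)/2 = +0.5, a false worsening. Using only the two rated concerns at both times, the change is 6 - 6 = 0 in the first case and 7.5 - 7.5 = 0 in the second.

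Treating non-matching concerns as missing under 5.2.5 alone would therefore spread this error to more visits. The two changes belong together.

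**The case against.** The best defence is that the text describes a sensible two-step process: a mismatch prompts review, and only visits judged incorrect are flagged. Excluding a visit for one mismatch is then not automatic, the benchmark is a fixed record (the Visit 1 form), and the review precedes database lock. This stands as far as it goes, but it leaves *incorrect* undefined and the unit still the visit. Review before lock does not help if the scores are already visible.

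A reader might infer that the review is unmasked. The SAP is silent. "This is a Phase 2, open-label study of the safety and tolerability" means that treatment is known, not that severity scores appear on the review listing.

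A reader might also infer that caregivers replace concerns that have resolved, so true benefit is understated. The documents do not support this. Both say that the Visit 1 concerns are re-rated, so a resolved concern should receive a low score. A mismatch could equally come from rewording, from a substitute rater (allowed by Protocol 9.5.9 in extenuating circumstances), or from a new and worse problem. Nor would concern-level matching cure such a bias. Suppose every other concern changes by -1 and one child in 10 has a resolved concern that would have changed by -7. Rating it gives ((-7 - 1 - 1)/3 + 9 × (-1))/10 = -1.2. Dropping the visit gives -1.0. Keeping the two matching concerns gives (-1 - 1)/2 = -1 for that child and again -1.0 overall. A percentage understatement built this way is no argument for the change.

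The statement "A treatment policy estimand will be used for all endpoints" helps only in part. A score for a different symptom is not an observation of the defined variable, so excluding that one score contradicts nothing. Discarding the matching ratings does sit poorly with it, because the same section says summaries use the observed data.

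Finally, the stakes are modest. There is no primary efficacy variable, tests are descriptive (SAP 5), Top 3 Concerns is one of 17 listed secondary variables, and it is not among the regression endpoints in 9.3.2. A flag removes only that child's Top 3 data at that visit.

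**Conclusion.** The point holds as a defect of rule and drafting. SAP 9.2.8 can remove a whole visit for one non-matching concern, pairs *may* with *will* without saying what separates them, does not define an incorrect concern, and does not specify whether scores are hidden. It is stricter than 5.2.5 and can delete matched ratings from domain analyses that the mismatch does not touch. Separately, the 5.2.5 average compares different sets of concerns at baseline and follow-up and can record a change where there was none: -1.0 in the example.

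The size is up to three ratings lost per affected visit where one would do. How many visits are affected cannot be known from the documents. The ratings count assumes one wrong concern per visit; the power figures assume random loss and borrow CGI-I effects. No direction or size of bias can be claimed. The change is cheap and worth making, on one descriptive secondary measure.

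**What to change.** In SAP 9.2.8, replace the visit-level flag with these rules:

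- Keep each rating whose concern matches the Screening form, and state what counts as a match.
- Treat a non-matching concern as missing under 5.2.5.
- Compute the change in average severity from the same concerns at baseline and follow-up, for blank and non-matching concerns alike. Each concern's baseline is the average of its own pre-dose ratings, in line with 5.2.4.
- Do the pre-lock matching on a listing of concern text without severity scores.
- Report the number of non-matching concerns per visit.

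The cost is a few sentences in the SAP, one listing and a small change to the derivation; no new data are needed. The downside is that some children contribute one or two concerns instead of three, so their averages are noisier. A Visit 1 concern that was not re-rated cannot be recovered; the mismatch counts show how often that happened.
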